## SYNOPSIS

NAME OF COMPANY: Achieve Life Sciences, Inc.
NAME OF INVESTIGATIONAL MEDICINAL PRODUCT (IMP): Cytisine 1.5 mg film-coated tablets
TITLE OF STUDY: Repeat-Dose Pharmacokinetic and Pharmacodynamic Evaluation of Cytisine in Healthy Smokers
PRINCIPAL INVESTIGATOR: [REDACTED]
STUDY CENTRE: Simbec Research Ltd (Simbec) [name]
CLINICAL PHASE: 1/2
OBJECTIVES: Primary: 

• To evaluate the pharmacokinetic (PK) parameters during repeat dosing of 1.5 mg or 3.0 mg cytisine when administered as the commercial 25-day schedule.

• To evaluate the pharmacodynamic (PD) effects (e.g. reduction in smoking) with repeat dosing of 1.5 mg or 3.0 mg cytisine when administered as the commercial 25-day schedule.

 Secondary: 

• To compare the PK parameters and tolerability for repeat dosing of 1.5 and 3.0 mg cytisine during the 25-day schedule in healthy smokers at 18-65 and >65 (elderly) years of age.

• To assess the renal elimination of cytisine via measurement of urinary concentrations of cytisine during treatment on Day 1 and Day 25.

• To evaluate for effects on QT/QTc interval prolongation and cardiac safety during treatment on Day 1 and Day 25 in healthy smokers at 18-65 and >65 (elderly) years of age.

METHODOLOGY: This is an open-label, randomised, multi-dose study to evaluate the PK profile and PD effect of cytisine when administered at doses of 1.5 mg and 3.0 mg following the commercialised 25-day schedule.
NUMBER OF SUBJECTS: A total of 36 subjects, such that 24 subjects are 18-65 years and 12 subjects are >65 years of age, will be randomised/enrolled to complete the study. An attempt will be made for 50% male and 50% female enrollment.
MAIN INCLUSION CRITERIA: Male or female smokers (minimum 10 cigarettes per day) aged 18 – 65+ years, with no allergy or

sensitivity to cytisine or any of its excipients, who are deemed healthy by meeting enrollment criteria and, unless surgically sterile, are willing to abstain from sexual intercourse or willing to use an effective method of contraception from the first dose and for 3 months after the last dose of cytisine (referred to as the IMP).

**IMP ADMINISTRATION:**

Each subject will receive the IMP (cytisine in the form of the commercial product [REDACTED], (1.5 mg or 3.0 mg dose cytisine) over a 25-day period according to the current [REDACTED] SmPC as follows:

Days	Regimen	Total Daily Dose		Approximate Interval
		1.5 mg Dose	3.0 mg Dose	
1-3	6 times daily	9.0 mg	18.0 mg	2 hours
4-12	5 times daily	7.5 mg	15.0 mg	2.5 hours
13-16	4 times daily	6.0 mg	12.0 mg	3 hours
17-20	3 times daily	4.5 mg	9.0 mg	4-5 hours
21-24	2 times daily	3.0 mg	6.0 mg	6 hours
25	Once daily	1.5 mg	3.0 mg	-

This schedule will require a total of 9 overnight stays (evenings of Day -1, Days 1, 2, 3 and Days 12, 16, 20, 24, and Day 25).

**CRITERIA FOR EVALUATION:**

**PK:**

***PK Endpoints:***

*Plasma:*

Estimated  $C_{max}$  values will be determined as follows:

- On Day 1, an estimate of  $C_{max}$  will be made after the first daily (morning) dose from venous blood samples collected immediately post dose at 00:30, 00:45, 01:00, 01:15, 01:30, and 02:00 hours. For the last evening dose on Day 1, Day 2, and Day 3, an estimate of  $C_{max}$  will be made from venous blood samples collected immediately post dose at 00:30, 01:00, 01:30, 02:00, 02:30, 03:00, 03:30, 04:00, and 05:00 hours.
- On Day 12, 16, 20, and 24, an estimate of  $C_{max}$  will be made after the last daily (evening) dose from venous blood samples collected immediately post dose at 01:00, 01:30, 02:00, 02:30, 03:00, 03:30 and 04:00 hours.

Estimated  $C_{min}$  values will be made from venous blood samples collected prior to the first morning dose on Day 4, Day 13, Day 17, Day 21 and Day 25.

On Day 25  $C_{max}$ ,  $T_{max}$ ,  $t_{1/2}$  and AUC will be determined after the administration of the final dose of cytisine from venous blood samples collected at the following timepoints: 00:30, 00:45, 01:00, 01:15, 01:30, 01:45, 02:00, 02:15, 02:30, 02:45, 03:00, 03:15, 03:30, 03:45, 04:00, 05:00, 06:00, 08:00, 10:00, 12:00 and 24:00 hours post-dose.

Total volume of blood drawn for the pharmacokinetic and clinical laboratory safety assessments will be up to approximately 328 mL per subject over a 26-day period.

*Urine:* Amount excreted in urine over 24 hours ( $A_e$ ) and percent of drug excreted in urine ( $A_e\%$ ) over 24 hours will be calculated on Day 1 and Day 25 of treatment.

**Safety:**

**Safety Endpoints:** The number of subjects with adverse events, serious adverse events, and adverse events leading to discontinuation will be documented. Adverse events will be assessed by clinical observation and spontaneous reporting by subjects. In addition, number of subjects with clinically significant abnormalities in vital signs (supine systolic/diastolic pressure, pulse and oral temperature), 12 lead ECG (heart rate, PR interval, QRS width, QT interval and QT interval corrected using Fridericia's (QTcF interval) formula), laboratory parameters (haematology, biochemistry and urinalysis) will be evaluated.

**STATISTICAL METHODS:**

All statistical analysis will be performed using SAS® version 9.3 or higher.

**Demographic and Background Data:** All demographic and background data will be listed. Demographic data will be summarised descriptively (age, height, weight and BMI) by dose group, age group and overall. Subject disposition and analysis sets (safety, PK, and PD) will also be listed and summarised by frequency.

**PK:** Pharmacokinetic parameters of cytisine will be derived from the plasma concentration-time profiles, by using a non-compartmental approach with a ln-linear terminal phase assumption. Actual times of sampling will be used.

The following pharmacokinetic parameters will be estimated: maximum observed plasma concentration ( $C_{max}$ ); minimum observed plasma concentration ( $C_{min}$ ); time of occurrence of  $C_{max}$  ( $T_{max}$ ); area under the plasma concentration versus time curve (AUC) from time zero (pre-dose) to the last sampling time with quantifiable concentrations ( $AUC_{0-t}$ ); AUC from time zero to infinity ( $AUC_{0-\infty}$ ); residual area or percentage of extrapolated part of  $AUC_{0-\infty}$  (%AUC); apparent terminal elimination rate constant ( $\lambda_z$ ); and apparent elimination terminal half-life ( $t_{1/2}$ ). In addition, the amount of cytisine excreted in urine over time ( $A_e$ ) and percent of drug excreted in urine ( $A_e\%$ ) will be derived from Day 1 and Day 25 24-hour urine collections.

**Safety:** All safety data will be listed.

AEs will be coded using Medical Dictionary for Regulatory Activities (MedDRA) version 20.0. The incidence of treatment emergent AEs (TEAE) will be summarised by organ system, preferred term, severity and relationship to study drug. Abnormal laboratory safety results will be listed.

**QT/QTc:** Triplicate ECGs, extracted at pre-dose and 0.5h, 1h, 2h, 3h, 4h, 6h, 8h, 12h and 24h after the first dose of cytisine on Day 1 and Day 25 will be obtained from the Holter recordings will be listed and analysed.

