**Figure 1: Marketed Dosing (1.5 mg tablet) and Timing schedule for [REDACTED]**

## 2.3. Recent Cytisine Pharmacokinetic Studies

### 2.3.1. Study CYT-BIO-02-07 in Healthy Subjects

The Phase 1 CYT-BIO-02-07 study enrolled 36 healthy male subjects who received a single oral dose of 1.5 mg cytisine under fasting conditions. Blood sampling and quantitative urine collection for the determination of cytisine in plasma and urine were performed at regular intervals during the treatment period. Physical examinations were performed by the Principal Investigator or designee at the pre-study screening, after admission to the clinical center, and during the evening before drug administration to the post-study examination just prior to discharge from the clinic. Vital signs (blood pressure, heart rate, and temperature) were also performed after admission to the clinical center, during the evening before drug administration, and within 30 min before drug administration (pre-dose), and 2, 4, 12, and 24 h after drug administration during the Treatment Period.

Blood sampling for determination of cytisine concentrations was carried out in the treatment period within 30 min before (pre-dose) and at 5, 10, 20, 30, 40, and 50 min and continued at 1.0; 1.25; 1.50; 1.75; 2.0; 2.25; 2.50; 3.0; 4.0; 5.0; 6.0; 8.0, and 10.0 h after administration of 1.5 mg cytisine (one [REDACTED] tablet). Urine was collected before (baseline) and quantitatively during the intervals 0-3, 3-6, 6-9, 9-12, and 12-24 h after administration of study drug. At the end of each collection interval, individual urine portions were pooled and aliquots were withdrawn from each urine pool. Creatinine concentrations were measured for each urine pool. Plasma and urine levels of cytisine were determined using validated LC-MS/MS analytical methods. Pharmacokinetic parameters of cytisine in plasma that were estimated included  $AUC_{last}$ ,  $AUC_{inf}$ ,  $C_{max}$ ,  $T_{max}$ , and  $T_{1/2}$ .

Results showed that no measurable plasma levels of cytisine were observed 5 min after drug administration. After 10 min, a level exceeding the limit of quantitation (LOQ) was noted in 5 of 36 (14%) subjects; after 20 min, a level exceeding the LOQ was noted in 29 of 36 (81%)

subjects. At 10 h after drug administration, the cytisine plasma levels exceeded LOQ in all subjects. Mean values and other calculated PK parameters are presented in [Table 1](#) (extracted from the Study CYT-BIO-02-07 report).

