**Figure 3: Study Design Overview**

The study will be comprised of a pre-study screen, followed by 25 days of treatment and a post-study follow-up.

**Screening (Day -28 to Day -1):** Screening assessments will be carried out within 28 days before first administration of cytisine (Section 11.2.1). Eligible subjects will then be asked to return on the evening prior to Day 1 (i.e. Day -1) for repeat of key entry testing, baseline questionnaires and provide overview of the risks of smoking and quit advice according to World Health Organization (WHO) guidelines (Section 11.2.2). Randomisation to treatment group will occur on the morning of Day 1 followed by initiation of study treatment.

**Treatment Period (Day 1 to Day 25):** Eligible subjects will take cytisine as outlined in the [redacted] product insert (SmPC). **NOTE:** Group A subjects take 1 tablet at each timepoint (1.5 mg), Group B subjects take 2 tablets at each timepoint (3.0 mg).

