### **8.6. Method of Assigning Subjects to Group A or Group B**

Subjects will be randomised to treatment dosing (1.5 mg or 3.0 mg) according to a code produced by [REDACTED] using the PROC PLAN procedure of SAS® version 9.1.3 or higher. Subjects will be numbered sequentially from 001 (i.e. 001, 002 etc.). Subjects will be stratified for age (elderly > 65 years: yes vs no) to assure that each treatment dosing has 6 elderly subjects and 12 non-elderly subjects. Replacement subjects will be assigned the same randomisation as the subject they are replacing, however, 100 will be added to the number (i.e., 101 would replace 001 etc.).

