## **11.2. Detailed Description of Study Visits**

### **11.2.1. Screening Visit (Day -28 to Day -2)**

All subjects will complete the following screening procedures within 28 days of Day 1 in order to verify required inclusion and exclusion criteria.

1. Written informed consent.
2. Document actual number of cigarettes smoked in the past 24 hours.
3. Expired CO.
4. Demographic data.
5. Medical history data.
6. Prior and concomitant medication.
7. Physical examination, including height and weight.
8. Vital signs (supine blood pressure, pulse rate and oral temperature).
9. 12-lead ECGs (triplicate).
10. Clinical laboratory safety tests (biochemistry, haematology, urinalysis, urine cotinine, virology, drugs of abuse, serum pregnancy for females and FSH for females of non-childbearing potential).
11. Verification of eligibility criteria.

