11.4.3.1 Statistical Analysis of PK Parameters

Dosing Schedule Comparison

The dosing schedule comparison analysis will be performed separately within each of the dose groups.

In order to perform comparisons between schedule changes within each dose group, following logarithmic transformation, C_{max} values (post-last dose on days 3, 12, 16, 20, 24 and 25), and C_{min} values (pre-first dose on days 4, 13, 17, 21 and 25) will be subjected to an analysis of variance (ANOVA) including a fixed effect for study day and a random effect of subject. Point estimates and 90% confidence intervals (CI) will be constructed for the contrasts between consecutive study days using the residual mean square error obtained from the ANOVA. The point and interval estimates will be back-transformed to give estimates of the ratios of the geometric least squares means (LSmean) and corresponding 90% CI. In addition, estimated geometric means will be presented. The analysis will be performed by age group (18-65 yrs, >65 yrs, all ages).

Dose Group Comparison

The dose group comparison will be a between-group analysis.

Following logarithmic transformation, C_{max} , AUC_{0-t} and AUC_{0-inf} values on Day 25 will be subjected to an analysis of variance (ANOVA) including a fixed effect for dose group. Point estimates and 90% confidence intervals (CI) will be constructed for the contrast between the 1.5 mg and 3.0 mg dose groups using the residual mean square error obtained from the ANOVA. The point and interval estimates will be back-transformed to give estimates of the ratios of the geometric least squares means (LSmean) and corresponding 90% CI. In addition, estimated geometric means will be presented. The analysis will be performed by age group (18-65 yrs, >65 yrs, all ages).

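### The Day 25 dose comparison leaves out body weight, which is already measured before randomisation, at an avoidable but probably modest cost in precision

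*Protocol*

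**What the plan says.** - **Dose.** Every subject takes one 1.5 mg tablet (Group A) or two (Group B) at each timepoint (protocol 5.1). Nothing is scaled to body size.
- **Population.** "An attempt will be made for 50% male and 50% female enrollment" (protocol synopsis). Protocol 6.1 and 6.2 contain no weight or BMI limit.
- **Weight.** It is recorded at screening: "Physical examination, including height and weight" (protocol 11.2.1). Its planned use is descriptive: "Demographic data will be summarised descriptively (age, height, weight and BMI) by dose group, age group and overall" (protocol synopsis; SAP 11.2.1 is similar).
- **Randomisation.** The only stratification factor is age, over 65 or not (protocol 8.6, SAP 3.6).
- **Model.** After log transformation, Cmax, AUC0-t and AUC0-inf "values on Day 25 will be subjected to an analysis of variance (ANOVA) including a fixed effect for dose group" (SAP 11.4.3.1). No other term is named, and the 90% CI uses that model's residual mean square. Protocol 15.7 describes the same comparison without a covariate.
- **Covariates.** SAP 10.2, the section on stratification and covariate adjustment, provides only for presentation by age group.
- **Status.** SAP 10.6 calls the comparison of dose groups the primary one of interest. Protocol 15.4 and SAP 3.5 describe the objectives as exploratory and plan no hypothesis test.

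**The concern.** This is the only modelled between-dose PK estimate in the plan, and it comes from about 18 subjects per arm. If exposure after a fixed dose depends on body size, the weight differences in an unrestricted mixed-sex sample go into the residual and widen the CI. A baseline covariate would remove that part without changing the ratio being estimated. Because no power or precision target is set, the width of this CI is the natural measure of what the comparison delivers.

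Timing also matters. The study is open-label, and SAP 9.3 has outputs for the younger cohort produced while elderly recruitment continues. An adjustment named now is prespecified; one added later would be chosen with data in view.

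**Working it through.** **Inputs from the documents.** There are 36 subjects: 2 × (12 + 6), or 18 per arm (protocol 15.4). The plan gives no precision calculation to reproduce. The CVs in protocol Table 1 do reproduce from its means and SDs: Cmax 6.55/15.55 = 42%, AUCinf 21.27/73.63 = 29%. They come from a study that "enrolled 36 healthy male subjects who received a single oral dose of 1.5 mg cytisine under fasting conditions" (protocol 2.3.1), so they are a proxy for Day 25 and contain no between-sex spread in weight.

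**Inputs not in the documents (assumed).** Log-weight SD 0.15 to 0.25, and exposure proportional to weight^-b with b from 0.5 to 1.0. The central case is 0.20 and 0.75. No effect of weight (R² = 0) is shown separately.

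**Step 1: planned CI.** s = sqrt(ln(1 + CV²)), which gives 0.284 (AUCinf) and 0.403 (Cmax). The log half-width is t(0.95, 34) × s × sqrt(2/18), with t = 1.691.
- AUCinf: 1.691 × 0.284 × 0.333 = 0.160, so ×/÷1.174. At a ratio of 2 the CI is 1.70-2.35.
- Cmax: 1.691 × 0.403 × 0.333 = 0.227, so ×/÷1.255. At a ratio of 2 the CI is 1.59-2.51.

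**Step 2: effect of one covariate.** With n per arm, the half-width is multiplied by t(0.95, 2n-3)/t(0.95, 2n-2) × sqrt((1 - R²) × (1 + 1/(2n-4))). Change in half-width:

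| R² | 18 per arm | 12 per arm | 6 per arm |
|---|---|---|---|
| 0 | +1.6% | +2.7% | +7.3% |
| 10% | -3.6% | -2.6% | +1.8% |
| 20% | -9.1% | -8.2% | -4.1% |
| 30% | -15.0% | -14.1% | -10.2% |
| Break-even R² | 3% | 5% | 13% |

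**Step 3: plausible R².** The assumed weight variance is added to the men-only variance. In the central case it is (0.75 × 0.20)² = 0.0225.
- AUC: R² = 0.0225/(0.0808 + 0.0225) = 22%, so the half-width is about 10% narrower. On this reckoning the unadjusted CI would be ×/÷1.199 and the adjusted one ×/÷1.177, or 1.67-2.40 against 1.70-2.35 at a ratio of 2.
- Cmax: R² = 0.0225/(0.1625 + 0.0225) = 12%, so 4-5% narrower: ×/÷1.274 against ×/÷1.260.
- Over the assumed range, R² is 7-44% for AUC (about 2-24% narrower) and 3-28% for Cmax (about 0-14% narrower).

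**Step 4: validity.** In simulations of 8,000 trials per setting, with b = 0 or 0.75 and 18 or 6 per arm, the unadjusted 90% CI covered the true ratio in 89-91% of trials.

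**The case against.** - **No evidence in the documents that weight matters.** This stands. A reader might take protocol 2.5, with its per-kg doses and 70 kg human, as showing that exposure depends on weight. It does not: that section converts animal doses to human equivalents and says nothing about variation among people. Protocol 2.3.1 reports about 64% of the dose excreted unchanged in urine within 24 h, which gives no weight relation either.
- **The analysis is valid.** This stands too. A reader might infer that chance differences in sex or weight bias the ratio. With 18 women among 36 and no sex stratum, the arms would differ by at least 4 women with probability 0.32 and by at least 6 with probability 0.09 (hypergeometric). In the central case, chance weight imbalance moves the ratio by an SD of about 5% (0.15 × sqrt(2/18) = 0.05). But randomisation makes this random error, and the unadjusted CI already allows for it. Counting it as a further harm would count it twice. The covariate proposed here also adjusts for weight, not for sex as such.
- **The gain can be overstated.** Dividing 0.0225 by the Table 1 variance alone gives R² = 28% for AUC, but that treats a men-only variance as if it already held the weight spread of a mixed-sex sample.
- **Little turns on the width.** No decision rule depends on it, post-hoc analyses are allowed, and SAP 11.2.1 tabulates weight, BMI and gender, so imbalance will be visible. This lowers the priority, but seeing an imbalance in a table does not recover precision.

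**Conclusion.** The point holds as avoidable loss of precision, not as bias or an invalid interval. The plan commits to a model with dose group only, although a relevant pre-randomisation measurement is in the database. Under the central assumptions the all-ages 90% CI would be about 10% narrower on the log scale for AUC and 4-5% for Cmax. The worst case is 1.6% wider, and break-even needs weight to explain only about 3% of the variance. These gains rest on an assumed weight spread, an assumed weight-exposure slope, and single-dose CVs in men carried over to Day 25. The severity is modest because the study is exploratory. The within-subject schedule comparison is not affected.

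**What to change.** In SAP 10.2 and the dose group comparison of SAP 11.4.3.1:

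- Prespecify ln(screening body weight) as a covariate in the all-ages Day 25 model, ideally with the age stratum used in randomisation, which that model also omits.
- Report the adjusted geometric mean ratio with its 90% CI, and the unadjusted ratio beside it.
- Keep the over-65 model (6 per arm) unadjusted, since break-even there is an R² of about 13%.
- State whether the 18-65 model (12 per arm, break-even about 5%) is adjusted, because it also feeds the interim outputs.

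The cost is a few words of text and one degree of freedom per added term. If weight explains nothing, the CI is about 1.6% wider. With a balanced age term as well and neither explaining anything, it is about 1.8% wider: t(0.95, 32)/t(0.95, 34) × sqrt(1 + 1/31) = 1.018. Exclusions from the PK Set would raise the break-even somewhat. No new data or visits are needed.

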**DURATION OF STUDY:**

Approximately 9 weeks for each individual (from screening to post-study follow-up).

## LIST OF ABBREVIATIONS AND DEFINITIONS OF TERMS

ABBREVIATION/TERM	DEFINITION
ADR	Adverse Drug Reaction
AE	Adverse Event
Ae	Amount excreted
ANOVA	Analysis of Variance
ALT	Alanine Aminotransferase
AST	Aspartate Aminotransferase
AUC 0-t	AUC from Time Zero to Last Sampling Time with Quantifiable Concentrations
AUC 0-∞	AUC from Time Zero to Infinity
%AUC	Residual Area or Percentage of Extrapolated Part of AUC 0-∞
BMI	Body Mass Index
C last	Last Quantifiable Concentration
C max	Maximum Observed Plasma Concentration
CRF	Case Report Form
CV	Coefficient of Variation
ECG	Electrocardiogram
EMA	European Medicines Agency
GCP	Good Clinical Practice
GMP	Good Manufacturing Practice
ICH	International Conference on Harmonization
IMP	Investigational Medicinal Product (for this protocol indicates cytisine 1.5 mg film coated tablet)
LC-MS/MS	Liquid Chromatography-tandem Mass Spectrometry
LLOQ	Lower Limit of Quantification
MedDRA	Medical Dictionary for Regulatory Activities
MHRA	Healthcare products Regulatory Agency
NCCIH	National Center for Complementary and Integrative Health (branch of US NIH)
PD	Pharmacodynamic
PK	Pharmacokinetics
RBC	Red Blood Cell Count
REC	Research Ethics Committee
SAE	Serious Adverse Event
SAR	Serious Adverse Reaction
SD	Standard Deviation
SmPC	Summary of Product Characteristics
SOC	(MedDRA) System Organ Class
SAP	Statistical Analysis Plan
SUSAR	Suspected Unexpected Serious Adverse Reactions
TEAE	Treatment emergent Adverse Events

---

ABBREVIATION/TERM	DEFINITION
$T_{\max}$	Time to Maximum Observed Concentration
$t_{1/2}$	Apparent Terminal Elimination Half-life
UADR	Unexpected Adverse Drug Reaction
UAE	Unexpected Adverse Event
ULOQ	Upper Limit of Quantification
WBC	White Blood Cell Count
$\lambda_z$	Apparent Terminal Elimination Rate Constant

## **1. ETHICS**

### **1.1. Research Ethics Committee**

This study protocol will be submitted to the Research Ethics Committee (REC) for review and approval. The approval of the REC must be obtained before commencement of any study procedures.

The favourable opinion is conditional upon the Sponsor registering the clinical trial in a publicly accessible database, within 6 weeks of the first participant recruited.

All substantial protocol amendments must be approved by the REC responsible for the study. Non-substantial amendments will not require prior approval by the REC.

If the study is stopped due to adverse events (AEs), it will not be recommenced without reference to the REC responsible for the study.

The outcome of the study (e.g. completed) will be reported to the REC responsible for the study within 90 days of completion of the last subject's final study procedures. In the event of the study being prematurely terminated, a summary safety report will be submitted to the REC responsible for the study within 15 days.

A summary of the clinical study report will be submitted to the REC responsible for the study within 1 year of completion of the last subject's final study procedures.

The REC will be informed that [REDACTED] is a commercial organisation and that the study is funded by Achieve Life Science. The subjects who take part in the clinical study will be paid for their inconvenience and have been informed that there may be no benefits gained by their participation. All potential conflicts of interest will be declared by the Principal Investigator and designees.

